## List of Abbreviations

Abbreviation	Term
24ssUAD	24-plex Serotype-specific urinary antigen detection
ARI	Acute Respiratory Infection
AUC	Area under the curve
ARGs	Antibiotic resistance genes
COMREC	College of Medicine Research and Ethics Committee
CRSU	Clinical Research Support Unit
GPCC	Gateway Primary Care Centre
LMICs	Low and Middle Income Countries
LSTM	Liverpool School of Tropical Medicine
MLW	Malawi Liverpool Wellcome Research Programme
NHC	Ndirande Health Centre
NHS	National Health Service
NPS	Nasopharyngeal Swab
PCVs	Pneumococcal conjugate vaccines
PERCH	Pneumonia Etiology Research for Child Health
QECH	Queen Elizabeth Central Hospital
QC	Quality control
ROC	Receiver Operating Characteristic
sSA	Sub Saharan Africa
ssUAD	Serotype-specific urinary antigen detection
SOPs	Standard Operating Procedures
UCL	University College London
UKHSA	UK Health Security Agency

[figure not shown]
MALAWI LIVERPOOL  
WELLCOME PROGRAMME

KAMUZU  
UNIVERSITY  
OF HEALTH SCIENCES

## Executive Summary

**Study type:** This is a nested case-control sub-study within the multi-site, observational NP Resistome study (COMREC reference P.10/24-1200).

**Problem:** Pneumococcal pneumonia is a leading cause of morbidity and mortality among children under five, especially in sub-Saharan Africa. Accurate diagnosis remains a challenge due to the need for invasive specimen collection and poor sensitivity of standard culture-based diagnostic tests, particularly after antibiotic use. Serotype-specific urinary antigen detection (ssUAD) offers a promising, non-invasive alternative for serotype surveillance and diagnosis of pneumococcal disease. Serotype-specific identification provided by ssUAD is crucial for monitoring the impact of vaccines and informing public health interventions. The ssUAD test is a Luminex-based urine antigen capture assay developed by the UK Health Security Agency (UKHSA) that targets 24 pneumococcal serotypes, with good sensitivity and specificity among adults with community-acquired pneumonia in the UK. Further investigation is required to determine its ability/utility to identify invasive disease among children, particularly in settings like sub-Saharan Africa, where high rates of asymptomatic carriage may affect diagnostic accuracy.

[figure not shown]
## Objectives

### Broad:

To evaluate the performance of the ssUAD test in detecting pneumococcal carriage and distinguishing it from invasive disease among children under five years old in Blantyre, Malawi.

### Specific:

1. To determine the prevalence of serotype-specific pneumococcal antigens in urine among children under five years of age with pneumonia compared to their healthy counterparts.
2. To characterise the association between the detection of serotype-specific antigens in urine and nasopharyngeal pneumococcal carriage among children.

MALAWI LIVERPOOL  
WELLCOME PROGRAMME

[figure not shown]

KAMUZU  
UNIVERSITY  
OF HEALTH SCIENCES

3. To define revised ssUAD thresholds that may distinguish pneumococcal carriage from disease, to support field evaluations and inform diagnostic and surveillance strategies in Malawi and similar settings.

**Methodology:** We will test 350 existing urine samples that have already been collected from children as part of the NP Resistome study (Protocol v5.0 COMREC reference P.10/24-1200), including healthy children in the community, children with pneumonia in the community, and children hospitalised with pneumonia at the time of recruitment. Participants of the NP Resistome study will be recruited from Ndirande Health Centre (NHC), Gateway Primary Care Centre (GPCC), and Queen Elizabeth Central Hospital (QECH) in Blantyre, Malawi. Urine samples will be aliquoted into 1.8 mL cryotubes and stored at -80°C at Malawi Liverpool Wellcome Research Programme (MLW) laboratory in Malawi. Aliquots from each urine sample will be tested using the ssUAD in the UK, as the assay is not currently available in Malawi. However, we are working towards developing and evaluating the assay locally as part of future implementation efforts. Urinary detection of pneumococcal serotypes will be compared with both culture-based and metagenomic sequencing results from nasopharyngeal swab (NPS) samples taken as part of the main study.

**Expected results and dissemination:** This sub-study will generate key data on the prevalence of pneumococcal serotype-specific urinary antigens in children with pneumonia and healthy controls. It will improve understanding of ssUAD performance as a surveillance tool in this setting, help distinguish antigenuria due to carriage from disease, and refine diagnostic thresholds for use in high-carriage and disease-burden settings. Study findings will inform surveillance, pneumonia diagnostics, and vaccine impact assessments in LMICs. Results will be shared with COMREC, the Blantyre District Health Office, at scientific conferences, both local and international, and in peer-reviewed publications.

MALAWI LIVERPOOL  
WELLCOME PROGRAMME

[figure not shown]

KAMUZU  
UNIVERSITY  
OF HEALTH SCIENCES

## 1.0 Background

*Streptococcus pneumoniae* (the pneumococcus) is a common commensal of the human nasopharynx, transmitted primarily through respiratory secretions. While typically asymptomatic during carriage, it serves as a prerequisite for the development of invasive disease. The pneumococcus causes a range of life-threatening infections, including pneumonia, meningitis, and bacteraemia, with a disproportionately high burden among children in sub-Saharan Africa (sSA). It remains a leading cause of childhood pneumonia worldwide. It contributes significantly to morbidity and mortality in children under five years of age, particularly in low- and middle-income countries (LMICs). Although the introduction of pneumococcal conjugate vaccines (PCVs) has significantly reduced the burden of vaccine-type disease, pneumonia caused by both vaccine and non-vaccine serotypes continues to present significant diagnostic challenges. These challenges stem from the reliance on invasive specimen collection, such as blood or endotracheal aspirates and the limited availability of sensitive diagnostic tools in resource-limited settings. Conventional culture-based methods are further hampered by low sensitivity, especially when antibiotics have been administered before specimen collection. These limitations undermine disease surveillance, leading to underestimation of the true burden of pneumococcal disease and the overall impact of vaccination programmes

Serotype-specific urinary antigen detection (ssUAD) has emerged as a promising non-invasive tool for diagnosing and serotyping pneumococcal pneumonia. The ssUAD test is a 25-plex Luminex-based extended-range urine antigen capture assay developed by UKHSA, which has shown favourable results for diagnosing pneumococcal disease among adult patients in the UK. The 24-serotype-specific urine antigen detection (24ssUAD) assay can detect pneumococcal capsular polysaccharide antigens in urine, offering greater diagnostic sensitivity than the culture-based method. The current version of ssUAD targets 24 pneumococcal serotypes and has a sensitivity of 96.2% and specificity of 89.9% among adults with community-acquired pneumonia or invasive pneumococcal disease in the UK. However, there is limited data on the surveillance and diagnostic performance of ssUAD in high-carriage and disease-burden settings, such as Malawi, where asymptomatic or healthy children may also shed pneumococcal antigens in urine, making it more challenging to distinguish invasive disease. Unpublished data from our testing of the 24ssUAD assay on historical urine samples from Malawian children

MALAWI LIVERPOOL  
WELLCOME PROGRAMME

KAMUZU  
UNIVERSITY  
OF HEALTH SCIENCES

[figure not shown]
with acute respiratory infection (ARI) indicate that pneumococcal antigens can be detected in urine, suggesting the assay's potential utility in such settings and highlighting the need for further evaluation to distinguish between carriage and disease. The data also revealed that pre-hospital antibiotic exposure significantly reduced the sensitivity of culture-based methods, decreasing pneumococcal detection rates from 81% to 21%, highlighting the potential diagnostic advantage of urine antigen assays in such contexts.

### 1.1. Literature Review

The accurate diagnosis of pneumococcal pneumonia remains a persistent challenge in both clinical and surveillance contexts, especially among young children in high-burden settings. Several studies have demonstrated that reliance on conventional microbiological diagnostics, such as blood culture, results in significant under-detection of pneumococcal infections due to their low sensitivity and the frequent use of antibiotics before hospital admission. In a systematic review by the Pneumonia Etiology Research for Child Health (PERCH) project, the limitations of blood culture sensitivity were particularly evident in children, where pathogen recovery was often below 10%.

These diagnostic limitations have prompted interest in antigen detection technologies, which are not reliant on viable organisms. Among these, the ssUAD assay has gained prominence. The ssUAD platform detects pneumococcal capsular polysaccharides in urine and allows for simultaneous serotyping of up to 24 pneumococcal serotypes using a multiplex Luminex-based platform. Studies conducted in adult populations in high-income countries have reported high sensitivity and specificity for the assay, particularly in cases of community-acquired pneumonia.

A critical advantage of ssUAD is its performance in patients who have received antibiotics. Multiple studies have reported that urinary antigen tests retain high diagnostic sensitivity even after antibiotic treatment, in contrast to sputum and blood cultures, which show significantly reduced positivity. Similarly, in studies involving hospitalised adults, both the BinaxNOW ICT and ssUAD assays were able to detect pneumococcal antigens in urine despite negative cultures due to prior antibiotic exposure. However, ssUAD appears to offer superior specificity and serotype information. In contrast, BinaxNOW does not provide serotype information and has

MALAWI LIVERPOOL  
WELLCOME PROGRAMME

KAMUZU  
UNIVERSITY  
OF HEALTH SCIENCES

been associated with false positives, particularly in settings with high pneumococcal carriage. This property makes ssUAD a particularly attractive diagnostic tool in LMICs, where empiric antibiotic treatment is often initiated before specimen collection.

Available evidence primarily comes from adult populations where nasopharyngeal colonisation is relatively uncommon and less likely to interfere with urine-based antigen detection. In contrast, children in sSA, including Malawi, often exhibit high nasopharyngeal carriage rates, which may make it difficult to distinguish between antigenuria due to invasive disease and antigen spillover from asymptomatic carriage.

[figure not shown]
Limited data exist on the specificity of ssUAD in high-carriage paediatric populations, particularly in low-resource settings where distinguishing between pneumococcal disease and antigenuria from asymptomatic carriage remains challenging. As such, there is an urgent need for context-specific data to define serotype-specific thresholds that can accurately differentiate carriage from disease. Addressing this gap is critical for the optimal use of ssUAD in clinical diagnostics, disease surveillance, and vaccine impact evaluations in high-burden LMIC settings.

## 1.2. Rationale

There is a critical need to improve pneumococcal pneumonia diagnostics and surveillance in LMICs where high nasopharyngeal carriage rates and frequent antibiotic use limit the utility of traditional culture-based methods. The ssUAD assay has the potential to fill this gap, but its diagnostic thresholds must be tailored to high-burden settings. By evaluating the prevalence and distribution of serotype-specific urinary antigens in children with and without pneumonia, and assessing how nasopharyngeal carriage influences antigen detection, this study will generate the evidence necessary to define thresholds that could distinguish carriage from disease. These data will guide the use of ssUAD in diagnostics, surveillance, and vaccine impact studies in LMICs.

### **1.3. Hypothesis**

We hypothesise that the ssUAD assay will show high sensitivity for detecting pneumococcal serotype-specific antigens in children with pneumonia, but background antigenuria due to asymptomatic carriage will necessitate revised thresholds for accurate disease attribution in this high-burden setting.

[figure not shown]

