### **2.6. Sample size:**

The minimum required sample size for this study is 147 urine specimens, accounting for a 10% allowance for non-response or data loss. This estimate is based on detecting a significant difference in pneumococcal serotype-specific antigen detection between children hospitalised with pneumonia, those treated at health centres, and healthy community controls.

[figure not shown]
The core sample size calculation indicates that at least 49 specimens per group are needed, assuming antigen detection rates of 70% in hospitalised children, 53% in health centre cases, and 35% in healthy controls, based on prior studies. Using a two-sided significance level of 0.05 and 80% statistical power, the estimated minimum total sample size is 147 participants across the three groups.

To address the limitation of a small sample size faced in our preliminary analysis of 214 urine specimens from hospitalised children, we plan to test all 350 urine specimens collected under the parent NP Resistome study. This expanded approach will improve the precision of our estimates, allow for subgroup analyses, and provide broader insights into pneumococcal antigen detection patterns across the study groups

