### **2.8.1. Prevalence and distribution (objective 1):**

Descriptive statistics (frequencies, means, medians) will be used to summarise participant characteristics across study groups. Serotype-specific prevalence of urinary pneumococcal antigens will be calculated for each group, hospitalised pneumonia, community-managed pneumonia, and healthy controls. Differences between groups will be assessed using chi-square tests or Fisher's exact test, as appropriate.

[figure not shown]

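### The hypothesis claims high sensitivity without a reference standard for pneumococcal pneumonia, and the planned case group makes the measured figure a mix of assay sensitivity, aetiology and carriage background

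*Protocol*

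**What the plan says.** Section 1.3 predicts that "the ssUAD assay will show high sensitivity for detecting pneumococcal serotype-specific antigens in children with pneumonia". It adds that antigen arising from asymptomatic carriage will call for revised thresholds before disease can be attributed accurately. It gives no numerical meaning for high and names no reference standard.

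The only sensitivity figure in the protocol is in 1.0 Background, where the assay "has a sensitivity of 96.2% and specificity of 89.9% among adults" with community-acquired pneumonia or invasive pneumococcal disease in the UK.

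Section 2.6 plans the study "assuming antigen detection rates of 70% in hospitalised children, 53% in health centre cases, and 35% in healthy controls".

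Under objective 1 (2.8.1), "Serotype-specific prevalence of urinary pneumococcal antigens will be calculated for each group", and groups are compared by chi-square or Fisher's exact test. Under objective 3 (2.8.3), a ROC analysis of signal intensity takes children with pneumonia as cases and healthy children as carriers. Its stated purpose is to find cut-offs that separate pneumococcal disease from carriage, and its findings are to be set against published UK data.

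**The concern.** Sensitivity is a proportion among children known to have the target condition. The protocol's microbiological comparators, culture and metagenomic sequencing of nasopharyngeal swabs, establish carriage and not the cause of the pneumonia. The case group in 2.8.3 is therefore all clinical pneumonia, while the target is pneumococcal disease. The protocol itself allows for other causes: its summary of the parent study (1.2.1) includes a viral PCR for pathogens of acute respiratory infection.

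At stake is how the main accuracy result will be read. A proportion of 50 to 70% labelled as sensitivity, placed beside 96.2% from UK adults as 2.8.3 invites, would look like assay failure in children. It could equally come from an excellent assay used in a group where many cases are not pneumococcal.

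**Working it through.** **Inputs from the protocol.** Detection rates of 70%, 53% and 35% (2.6); adult sensitivity 96.2% and specificity 89.9% (1.0); 350 specimens (2.6). The protocol states no sensitivity for children, so there is no such figure to reproduce. Nothing below depends on the minimum of 49 per group.

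**Assumptions.** The 2.6 rates are read as positivity for any serotype at the existing cut-off. The protocol does not give the pneumococcal share of cases, *f*, or the positivity among non-pneumococcal cases, *b*. Both are varied.

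**Step 1. Apparent sensitivity with all pneumonia as diseased.** This is simply the detection rate: 70% hospitalised, 53% health centre, and (0.70 + 0.53)/2 = 61.5% pooled with equal groups. Raising a cut-off cannot turn a negative specimen positive, so thresholds raised to exclude carriage antigen can only reduce these figures or, at best, leave them unchanged.

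**Step 2. What those rates imply about true sensitivity.** Expected positivity in cases is p = f × Se + (1 − f) × b, so f = (p − b)/(Se − b). With Se = 0.962 and b = 0.35, the healthy-control rate:

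- hospitalised: (0.70 − 0.35)/(0.962 − 0.35) = 0.35/0.612 = 0.57
- health centre: (0.53 − 0.35)/0.612 = 0.18/0.612 = 0.29

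Over a range of backgrounds, still with Se = 0.962:

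| Background b | f, hospitalised | f, health centre |
|---|---|---|
| 0.35 | 0.57 | 0.29 |
| 0.20 | 0.66 | 0.43 |
| 0.101 (1 − 0.899) | 0.70 | 0.50 |
| 0 | 0.73 | 0.55 |

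Every row is compatible with the planning rates and a sensitivity of 96.2%.

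**Step 3. How far the figure moves with aetiology alone.** Holding Se = 0.962 and b = 0.35, positivity in cases is 53.4% at f = 0.3, 65.6% at f = 0.5, 77.8% at f = 0.7 and 96.2% at f = 1. The assay is identical in all four.

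**Step 4. What the data can support.** The prevalence difference from healthy children is 0.70 − 0.35 = 35 percentage points in hospital and 0.53 − 0.35 = 18 points at health centres. The attributable fraction, AF = (p_case − p_healthy)/(1 − p_healthy), is 0.35/0.65 = 53.8% and 0.18/0.65 = 27.7%.

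For precision, let R = (1 − p_case)/(1 − p_healthy), so that AF = 1 − R, with SE(log R) = √[p_case/(n(1 − p_case)) + p_healthy/(n(1 − p_healthy))]. Group sizes are not stated, so equal splits of 350 are assumed:

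| n per group | AF hospitalised, 95% CI | AF health centre, 95% CI |
|---|---|---|
| 117 (350/3) | 37 to 66% | 9 to 43% |
| 88 (350/4) | 34 to 68% | 5 to 45% |

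The AF formula is Step 2 with Se = 1. At Se = 0.962 the pneumococcal shares are 57% and 29% instead of 54% and 28%, so the result is not sensitive to that simplification. It depends much more on the background.

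**The case against.** The strongest reply is that 2.6 gives detection rates and never calls them sensitivities, and that Step 2 shows they are compatible with near-perfect sensitivity. This stands. A reader might infer that the hypothesis contradicts the planning rates, but the documents do not support that.

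A reader might also infer that even a perfect test would fail the hypothesis. That needs a pass mark for high and a pneumococcal share, and the protocol gives neither. The 54% and 28% in Step 4 rest on an assumed background. Read literally, 1.3 concerns finding antigen in these children, and a perfect assay would not fail on that reading.

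Nor must the two halves of 1.3 conflict. They can be read in sequence: high sensitivity at the existing cut-off, then a trade for specificity.

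Three further points are fair. Sensitivity against nasopharyngeal carriage could be computed, although it is not sensitivity for disease. Section 2.8.1 already compares pneumonia with healthy children, so the excess over background is implicit in planned output; only the effect measure is missing. And no planned test or sample-size input uses the phrase high sensitivity.

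The mismatch in 2.8.3 remains. A ROC curve plots sensitivity against one minus specificity, so any cut-off chosen from it carries a sensitivity, here computed among all pneumonia while the stated target is pneumococcal disease. The protocol fixes both the hypothesis and the case group, so this is not a detail left to an analysis plan.

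**Conclusion.** The point holds in a limited form. As a claim about pneumococcal disease, the hypothesis cannot be confirmed by the planned analyses, because there is no reference standard for pneumococcal pneumonia and no criterion for high. On the planned denominator the protocol's own rates give about 70% and 53% at the existing cut-off, and lower after upward revision. Those figures say little about the assay: they fit 96.2% sensitivity with pneumococcal shares of about 57% and 29% at a 35% background, or up to 73% and 55% with no background. They are not comparable with the UK adult figure.

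This is a problem of estimand and interpretation. It does not show that the assay will perform poorly or that the samples are inadequate. The size of the effect depends on the planning rates holding and on the assumed background.

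**What to change.** - **1.3:** replace the sensitivity claim with one the data can test, namely that antigen detection at the existing cut-off is more frequent in children with pneumonia than in healthy children.
- **2.8.3:** report the share of clinical pneumonia above a cut-off as detection in clinical pneumonia, not as sensitivity for pneumococcal disease, and state that it will not be compared directly with the UK sensitivity.
- **2.8.1:** for each pneumonia group, add the prevalence difference from healthy children and the attributable fraction (p_case − p_healthy)/(1 − p_healthy), each with a 95% confidence interval. State the assumption that non-pneumococcal cases share the healthy background.

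The cost is small: rewording in two sections and one further estimate from data already planned, with no new specimens or tests. The drawback is that the attributable fraction is only as good as the background assumption, which these data cannot verify.

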### **1.4. Study Objectives**

#### **1.4.1. Broad objective**

To evaluate the performance of the ssUAD test in detecting pneumococcal carriage and distinguishing it from invasive disease among children aged 12-24 months with pneumonia, compared to healthy children, in Blantyre, Malawi.

#### **1.4.2. Specific objectives**

1. Determine the prevalence of serotype-specific pneumococcal antigens in urine among children under five years of age with pneumonia compared to healthy counterparts.

MALAWI LIVERPOOL  
WELLCOME PROGRAMME

KAMUZU  
UNIVERSITY  
OF HEALTH SCIENCES

2. To characterise the association between the detection of serotype-specific antigens in urine and nasopharyngeal pneumococcal carriage among children.
3. To define revised ssUAD thresholds that distinguish pneumococcal carriage from disease, to support field evaluations and inform diagnostic and surveillance strategies in Malawi and similar settings.

## 2.0 Methodology

### 2.1. Study Design and Setting:

This case-control sub-study is nested within the NP Resistome study (Protocol v5.0 COMREC reference P.10/24-1200), a prospective observational cohort conducted in Blantyre, Malawi. Recruitment will take place at Ndirande Health Centre (NHC), Gateway Primary Care Centre (GPCC), and Queen Elizabeth Central Hospital (QECH). The sub-study will involve the analysis of urine samples that have already been collected from children aged 12–24 months across four defined participant groups in the parent NP Resistome study.

[figure not shown]
Study Population:

Participants will be children aged 12–24 months enrolled in the NP Resistome study (COMREC reference P.10/24-1200) in the following groups;

- Children hospitalised with pneumonia at QECH.
- Children with pneumonia treated at primary health centres (i.e NHC).
- Healthy community controls with and without recent antibiotic exposure.

